3.3 Key secondary efficacy outcome variables

3.3.1 Proportion of participants who remain relapse-free up to Week 36

The proportion of participants who remain relapse-free up to Week 36 will be analyzed as a binary response variable, where participants who remain relapse-free throughout the study up to Week 36 will be considered responders, but otherwise participants will be considered non-responders.

Relapse is defined as the appearance of: 3 or more new lesions per month (blisters, eczematous lesions, or urticarial plaques); or at least one large (> 10 cm diameter) eczematous lesion or urticarial plaques that do not heal within 1 week; or the extension of established lesions or daily pruritus in participants who have achieved disease control.

Details regarding collection of BP disease state clinical assessments and handling of missing data have been reported in Section [3.2](#).

Participants who need to increase their OCS dose as a rescue therapy to treat their BP after having previously achieved disease control, those who receive medications deemed to be intercurrent events as per Section [3.1.5.2](#), and those who withdraw from the study will be considered as not being relapse free up to week 36 (i.e. non responders in the analysis).

A supportive analysis of the time to first BP relapse will also be performed in order to explore the timing of relapse events.

The time (weeks) from randomization to the first BP relapse is defined as follows:

$$(date \text{ of } first \text{ relapse} - date \text{ of } randomization + 1) / 7$$

Participants who receive medications deemed to be intercurrent events as per Section [3.1.5.2](#) will be considered with a relapse on the date of start of restricted medications.

Participants who need to increase their OCS dose as a rescue therapy to treat their BP after having previously achieved disease control will be considered with a relapse on the date of OCS dose increase recorded with start date $>$ date of disease control assessment.

For restricted medications/OCS during the study missing/partial start dates are not allowed.

Participants who withdraw from the study or are lost to follow-up before the Week 36 assessment and don't have a relapse or a change in medications as described above will be considered as not-relapse free the day after their last available assessment showing them to be relapse-free.

Participants with missing data for any other reason will be considered as not-relapse free.

The time from randomization to the first BP relapse for participants who do not experience any relapse will be censored at their last available assessment showing them to be relapse-free. The same intercurrent events as detailed above in this section will be applied.

All the data in the double-blind period will be included.

3.3.2 Cumulative OCS exposure (mg/kg) from baseline to Week 36 and from baseline to Week 16

Details about OCS usage will be collected at each scheduled visit by the Investigator as reported in Section [3.1.5.1](#).

Cumulative OCS exposure (mg/kg) from baseline to Week 36 and from baseline to Week 16 will be calculated for each participant over 4 weekly intervals.

For each visit from Visit 4 (Week 4) until Visit 13 (Week 36), excluding Visit 5 (Week 6), the OCS exposure (mg/kg) will be computed by summing the recorded doses taken during each day over the past 28 days, thus the day of the visit will not be included. It will be calculated using the 28 days prior to the day of the scheduled visit. No visit window will be applied to the scheduled visit day.

For Visit 13 (Week 36), if the 4 weekly interval based on the scheduled visit day is including any days after the actual Visit 13 (Week 36) day (ie, days in the OLE period) the 4 weekly OCS exposure will be computed by summing the recorded doses taken during only the days during the double-blind period and rescaling them into a 4 weekly interval. For example, if the Visit 13 (Week 36) 4 weekly interval includes only 25 days in the double-blind period, it will be computed by summing the recorded doses taken during these 25 days, dividing by 25 and multiplying per 28. If less than 14 days are in the double-blind period, the Visit 13 (Week 36) 4 weekly interval will be considered with missing data of OCS exposure.

More details on OCS daily exposure are reported in Section [3.1.5.1](#).

To compute the dose in mg/kg for each day of OCS assumption the baseline weight will be considered.

The set of intercurrent events for this estimand consists of participants who receive medications deemed to be intercurrent events as per Section [3.1.5.2](#) and participants who withdraw from the study. These events will be handled with an effectiveness strategy, including all available data in a Mixed-effect Model for Repeated Measures (MMRM) until the occurrence of such events. This avoids making potentially implausible imputation assumptions around future OCS use that a composite strategy would involve. For example, for a participant who discontinues at a high daily OCS dose early in the study, imputing a high daily OCS dose for the remainder of the treatment period would result in an imputed

cumulative OCS dose higher than participants would ever realistically receive. Likewise, using a treatment policy strategy is also not considered appropriate, as the use of restricted medications would confound future OCS use. For example, if OCS were discontinued to receive another treatment due to lack of response or intolerance to OCS, the treatment policy approach would show a low cumulative OCS dose, which is a positive outcome and does not fairly represent the overall picture.

Participants who receive medications deemed to be intercurrent events as per Section 3.1.5.2 will be considered with missing OCS exposure (mg/kg) from the date of start of restricted medications. Hence for the 4 weekly interval that includes this date, the OCS exposure will be computed by summing the recorded doses taken during only the days before the start of the restricted medications and rescaling them into a 4 weekly interval. For restricted medications during the study missing/partial start dates are not allowed.

Participants who withdraw from the study will be considered with missing OCS exposure (mg/kg) starting from the last contact with the participant. Hence the 4 weekly interval that includes this, the OCS exposure will be computed by summing the recorded doses taken during only the days before the last contact and rescaling them into a 4 weekly interval.

Note that the list of intercurrent events does not include increases in OCS dose after achieving disease control, and all doses of OCS will be included in the derivation of cumulative OCS exposure from baseline to Week 36/Week 16.

3.3.2.1 Cumulative actual OCS exposure (mg) from baseline to Week 36 and from baseline to Week 16

Cumulative actual OCS exposure (mg) from baseline to Week 36 and from baseline to Week 16 for each participant over 4 weekly intervals, will be also computed as additional endpoint analysed in an exploratory way.

The same derivation rules and intercurrent events described in Section 3.3.2 will be applied.

3.3.2.2 Daily OCS dose (mg/kg/day) from baseline to Week 36

Daily OCS dose (mg/kg/day) will be computed for each participant as average daily dose over weekly intervals and will be analysed descriptively as an additional endpoint.

For each week, from Week 4 to Week 36, the average daily OCS dose (mg/kg/day) will be computed as the mean of the recorded doses taken during the past 7 days, thus the day of the visit will not be included. It will be calculated using the 7 days prior to the day of the scheduled visit. No visit window will be applied to the scheduled visit day.

For Visit 13 (Week 36), if the weekly interval based on the scheduled visit day is including any days after the actual Visit 13 (Week 36) day (ie, days in the OLE period) the weekly

average daily OCS dose will be computed by including only the days during the double-blind period in the mean computation.

More details on OCS daily exposure are reported in Section 3.1.5.1.

To compute the dose in mg/kg for each day of OCS assumption the baseline weight will be considered.

The same derivation rules and intercurrent events described in Section 3.3.2 will be applied.

3.3.3 Change from baseline in BPDAI activity score at Week 36

BPDAI activity score is a continuous endpoint that will be completed at the visits specified in the CSP Table 2 and it is part of the Bullous Pemphigoid Disease Area Index assessment.

The Bullous Pemphigoid Disease Area Index is a clinician completed tool that is used for independent disease severity assessment to measure disease extent in BP.

The Investigator will be required to complete the BPDAI at every visit during double-blind and OLE as specified in the CSP Table 2.

The BPDAI tool computes 2 scores: total BPDAI activity and total BPDAI damage.

The total BPDAI activity score (0 to 360) is the arithmetic sum of the 3 subcomponents – cutaneous blisters/ erosions, cutaneous urticaria/erythema, and mucosal blisters/ erosions. If any of the scores are missing the total BPDAI activity score is considered missing.

The total BPDAI damage score (0 to 12) is the arithmetic sum of the items rated regionally for damage caused by more permanent features such as post-inflammatory hyperpigmentation, scarring and other. If any of the items rate is missing the total BPDAI damage score is considered missing.

The BPDAI quantifies lesion number and size thresholds. Lesions are rated based on the regions affected. BPDAI gives additional weighting to areas of the skin primarily affected in BP, such as the limbs, and less emphasis to scalp and face. The BPDAI total activity and BPDAI damage give an indication of disease activity, with higher scores indicating greater disease activity or damage.

The change from baseline in the total BPDAI activity score at Week 36 will be analysed as key secondary endpoint, while the change in the total BPDAI damage score will be summarized descriptively.

Figure 2 **Bullous Pemphigoid Disease Area Index Tool (Murrell et al 2012)**

BPDAI		ACTIVITY		ACTIVITY		DAMAGE							
SKIN													
Anatomical location		Number of Lesions if <3		Urticaria/ Erythema / Other		Number of Lesions if <3							
Erosions/Blisters		Pigmentation / Other											
0 absent		0 absent		Absent 0, present 1									
1 1-3 lesions, none > 1 cm diameter		1 1-3 lesions, none >6 cm diameter											
2 1-3 lesions, at least one > 1 cm diameter		2 1-3 lesions, at least one lesion > 6 cm diameter											
3 >3 lesions, none > 2 cm diameter		3 >3 lesions, or at least one lesion > 10 cm											
5 >3 lesions, and at least one >2 cm		5 >3 lesions and at least one lesion > 25 cm											
10 >3 lesions, and at least one lesion >5 cm diameter or entire area		10 >3 lesions and at least one lesion > 50 cm diameter or entire area											
Head													
Neck													
Chest													
Left arm													
Right arm													
Hands													
Abdomen													
Genitals													
Back/Buttocks													
Left leg													
Right leg													
Feet													
Total skin		/120		/120									
MUCOSA		Erosions/Blisters											
1 1 lesion													
2 2-3 lesions													
5 >3 lesions, or 2 lesions >2cm													
10 entire area													
Eyes													
Nose													
Buccal mucosa													
Hard palate													
Soft palate													
Upper gingiva													
Lower gingiva													
Tongue													
Floor of Mouth													
Labial Mucosa													
Posterior Pharynx													
Anogenital													
Total Mucosa		/120											

Any participant with missing data at a specific time point will be considered as having a missing score at that time point.

The set of intercurrent events for this estimand consists of participants who use restricted medications, participants who have their OCS dose increased as rescue therapy after having previously achieved disease control and participants who withdraw from the study.

Participants who receive medications deemed to be intercurrent events as per Section [3.1.5.2](#) will have their last BPDAI activity score observed prior to the date of start of restricted medication carried forward to Week 36. If baseline is the last available assessment prior to the date of start of restricted medication, then it will be used to impute the missing data.

Likewise, participants who need to increase their OCS dose as a rescue therapy to treat their BP after having previously achieved disease control will have their last BPDAI activity score observed prior to the date of OCS dose increase recorded with start date > date of disease control assessment carried forward to Week 36. If baseline is the last available assessment prior to the date of OCS dose increase, then it will be used to impute the missing data.

For restricted medications/OCS during the study missing/partial start dates are not allowed. For participants who withdraw from the study without having rescue or restricted medications, missing BPDAI activity score at Week 36 will be imputed using multiple imputation based on participants who don't have rescue/restricted medication use. The same approach will be applied to those participants with missing data at Week 36 for any other reason. Further details are provided in Section [4.2.7.3](#). For the summary statistics, missing values will remain missing.

3.3.4 Change from baseline in BPDAI-Pruritus score at Week 36

The BPDAI-Pruritus is a continuous endpoint that will be completed at the visits specified in the CSP Table 2.

The BPDAI-Pruritus is a separate component of the BPDAI that asks the participant to grade the severity of pruritus over the past 24 hours, the past week, and the past month. For each recall period, severity of pruritus is rated on an NRS ranging from 0 for no itch to 10 for maximal itching.

The BPDAI-Pruritus score will be computed as the sum of the three components ranging from 0 to 30.

The change from baseline in the BPDAI-Pruritus score at Week 36 will be analysed as a key secondary endpoint.

Any participant with missing data at a specific time point will be considered as having missing severity of pruritus at that time point.

The set of intercurrent events, the estimand approach and the imputation rules are the same as described in Section 3.3.3 for the change from baseline in BPDAI activity score at Week 36.

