#### 4.1.2 Double-blind Treatment Period

Approximately 120 eligible participants will be randomized 1:1 at baseline (Visit 2), to receive either benralizumab or placebo every 4 weeks (Q4W) by subcutaneous (SC) injection.

The randomization will be stratified by disease severity and time of BP diagnosis (participants with newly diagnosed BP; participants with a previous diagnosis of BP who have relapsed). Bullous pemphigoid disease area index (BPDAI) activity score will be used to assess disease severity, whereby participants with a score greater than or equal to 56 points will be classified as severe. The double-blind treatment period for each participant will last for 36 weeks.

Participants will receive a loading dose of either 60 mg benralizumab or placebo, administered as 2 SC injections at Visit 2. After 4 weeks, participants will receive 30 mg benralizumab or placebo Q4W per their initial randomization until the end of the double-blind treatment period. Starting at Visit 2, participants will also receive OCS 0.5 mg/kg/day until BP disease control is achieved. In participants who do not achieve disease control, the OCS dose can be increased (eg, 0.75 mg/kg; [\(Feliciani et al 2015\)](#) to achieve disease control. The steroid doses and time necessary to achieve disease control of BP may vary between participants.

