The primary endpoint chosen is to assess the effect of benralizumab on sustained disease remission. This endpoint was chosen based on outcome measures recommended by the consensus statement ([Murrell et al 2012](#)) and feedback from a panel of clinical experts on BP who were consulted on the feasibility of using benralizumab as a treatment for BP and on the optimal study design. While OCS are the only well-established treatment for BP and highly effective for achieving disease control, the relapse rate is high on tapering and discontinuation, and OCS are associated with significant morbidity and mortality. The overall treatment goal in participants with BP is to reduce the dose of OCS and associated side effects while maintaining disease control. The ability of participants to taper steroids and achieve complete remission off steroids (the proposed primary variable) and the proportion of participants who have relapsed after tapering steroid therapy (the first key secondary variable) are therefore clinically important outcomes in this participant population. Both are accepted endpoints for BP studies ([Murrell et al 2012](#)). The key secondary variables, proportion of participants who remain relapse-free up to Week 36, cumulative OCS exposure (mg/kg) up to Week 16 and up to Week 36, and change in BPDAI activity and pruritus scores at Week 36, will also provide an opportunity to assess benralizumab's efficacy in participants with symptomatic BP.

The OLE will provide an opportunity to assess long-term safety and tolerability, in addition to assessing efficacy of benralizumab monotherapy, and to ensure that all participants who complete the double-blind treatment period can have access to treatment with benralizumab.

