### 8.1.1.1 Bullous Pemphigoid Disease State

Investigators will be asked to make a clinical assessment of the participants to determine their BP disease state (ie, active disease, disease control, end of consolidation phase, remission, and relapse) from baseline (Visit 2) until the end of the double-blind period, during the OLE, and then in addition at the IPD, and follow-up visit. The BP disease state will be considered "active disease" until one of the disease states in [Table 6](#) is achieved.

At each visit, investigators will be required to assess a participant's outcome measures, including the states defined in [Table 6](#). The outcome measure will be documented in the eCRF.

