**Table 10 Primary and Key Secondary Estimands**

Statistical category	Treatment condition	Endpoint (Population)	Intercurrent event strategy	Population level summary (Analysis)
Key Secondary	Treatment with benralizumab versus placebo, regardless of IP compliance; rescue with OCS and restricted medication use indicate treatment failure	Change from baseline in BPDAI activity score at Week 36, change from baseline in BPDAI-Pruritus score at Week 36 (FAS)	

• Treatment discontinuation – treatment policy

• Rescue with OCSa – composite (LOCF)

• Restricted medication use – composite (LOCF)

• Study withdrawal – hypothetical (multiple imputation)

	Difference in mean change from baseline in BPDAI activity score/BPDAI-Pruritus score at Week 36 (ANCOVA)

a Rescue with OCS is defined as needing to increase OCS dose after previously having achieved disease control.

ANCOVA, analysis of covariance; BP, bullous pemphigoid; BPDAI, bullous pemphigoid disease area index; FAS, full analysis set; IP, investigational product; LOCF, last observation carried forwards; MMRM, mixed-effect model for repeated measures; OCS, oral corticosteroids.

The amount of missing data for this study is expected to be low, as participants who prematurely discontinue IP will be asked to come in for all visits and complete all study assessments up to the end of the study. Any participant with missing data at a specific time point will be considered as a non-responder at that time point.

Further estimands will be specified for the primary and key secondary endpoints to carry out sensitivity analyses for assessing the robustness of results. These sensitivity analyses will explore different methods for handling intercurrent events and different assumptions for missing data. Further description is given in Section 9.4.8 and will be fully specified in the SAP.

All analyses for the OLE endpoints will be descriptive, as no placebo-control data will be available for this period. Consequently, no hypothesis testing will be performed.

Demography and baseline characteristics will be summarized by treatment for the FAS. If there are major differences between the FAS and the safety analysis set, the summaries will be repeated and presented for the safety analysis set.

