#### **9.4.2.2 Analysis Methods for Key Secondary Efficacy Variables**

##### **Proportion of participants who remain relapse-free up to Week 36**

The proportion of participants who remain relapse-free up to Week 36 will be analyzed as a binary response variable, where participants who remain relapse-free throughout the study up to Week 36 will be considered responders, but otherwise participants will be considered non-responders. Relapse is defined as the appearance of: 3 or more new lesions per month (blisters, eczematous lesions, or urticarial plaques); or at least one large ( $> 10$  cm diameter) eczematous lesion or urticarial plaques that do not heal within 1 week; or the extension of established lesions or daily pruritus in participants who have achieved disease control.

The estimand strategy is outlined in [Table 10](#) above. Intercurrent events of rescue use with OCS after having previously achieved disease control, restricted medication use, and study withdrawal are unfavorable outcomes and will be handled with a composite strategy whereby participants experiencing these events prior to Week 36 will be considered as non-responders (ie, not relapse-free) in the analysis. Likewise, participants with missing data at Week 36 for any other reason will be considered as not-relapse free.

For the primary analysis of the proportion of participants relapse-free at Week 36, a logistic regression model will be fitted using a logit link function. The model will include treatment, baseline disease severity (moderate or severe, with a BPDAI activity score of 56 points used as the threshold between moderate and severe) and time of BP diagnosis (ie, participants with newly diagnosed BP versus participants with a previous diagnosis of BP who have relapsed) as categorical covariates.

The model will be used to estimate the proportion who are relapse-free for benralizumab and placebo, the difference between these proportions (benralizumab – placebo), a rate ratio

(benralizumab/placebo), and an odds ratio, with corresponding 95% confidence limits. A p-value, corresponding to a 2-sided test, will be presented to compare the benralizumab and placebo treatment groups. Note that if the logistic regression model does not converge to a solution due to low response rates in certain categories, the endpoint will be analyzed using a Cochran–Mantel–Haenszel test.

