3.2 Primary outcome variable

The primary outcome variable is a binary response whereby participants will be classified as responders if they are in complete remission while off OCS for ≥ 2 months at Week 36. Otherwise, participants will be classified as non-responders.

Investigators will be asked to make a clinical assessment of the participants to determine their BP disease state (ie, active disease, disease control, end of consolidation phase, remission, and relapse) from Visit 2 until the end of the double-blind period, during the OLE period, and then in addition at the IP Discontinuation (IPD), End of Treatment (EOT) and follow-up visit.

At each visit, Investigators will be required to assess a participant's outcome measures, including the states defined in Table 4. The outcome measure will be documented in the eCRF.

Table 4 Definitions for Bullous Pemphigoid Outcome Measures

Outcome measure	Definition ^b
Disease control/beginning of consolidation phase	The time at which new lesions cease to form and established lesions begin to heal or pruritic symptoms start to abate
End of consolidation phase	Time at which no new lesions have developed for a minimum of 2 weeks and approximately 80% of lesions have healed and pruritic symptoms are minimal
Sustained partial remission on minimal steroid ^a /off steroid therapy	The presence of transient new lesions that heal within 1 week while the participant is on minimal steroid therapy or off steroid therapy for at least 2 months
Sustained complete remission on minimal steroid ^a /off steroid therapy	The absence of new or established lesions or pruritus while the participant is on minimal steroid therapy/off steroid therapy for at least 2 months
Relapse	The appearance of 3 or more new lesions per month (blisters, eczematous lesions, or urticarial plaques) or at least one large (> 10 cm diameter) eczematous lesion or urticarial plaques that do not heal within 1 week, or the extension of established lesions or daily pruritus in participants who have achieved disease control

^b Minimal steroid therapy is defined as less than or equal to 0.1 mg/kg/day of prednisone or equivalent

^c Definitions as per [Murrell et al 2012](#)

Each BP disease state clinical assessment collected during any scheduled/ unscheduled/ IPD/ EOT/ follow-up visits will be included in the Week 36 visit as per adjusted defined visit window, see Section [3.1.4](#), and analysed accordingly.

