The time (weeks) from randomization to disease control is defined as follows:

$$(date\ of\ first\ assessment\ of\ disease\ control - date\ of\ randomization + 1) / 7$$

Participants who do not reach disease control will be reported as having missing time to disease control.

For the Kaplan Meier analyses, the time from randomization to disease control for participants who do not reach disease control will be censored at the date of the Week 36 assessment for participants who complete the double-blind period. Participants who withdraw from the study

or are lost to follow-up before the Week 36 assessment will be censored at the last visit date after which disease state could not be assessed (ie, at the last non-missing disease state clinical assessment).

OCS dose (mg/kg) at disease control will be calculated for each participant as the dose recorded by the Investigator as per Section 3.1.5.1 on the day before the clinical assessment of disease control.

To compute the dose in mg/kg the baseline weight will be considered.

The handling of partial/missing dose or dates for OCS is detailed in Section 3.1.5.1.

The end of the consolidation phase is defined as the time at which no new lesions have developed for a minimum of 2 weeks and approximately 80% of lesions have healed and pruritic symptoms are minimal, as per Investigator assessment.

The time (weeks) from randomization to end of the consolidation phase is defined as follows:

$(\text{date of end of the consolidation phase} - \text{date of randomization} + 1) / 7$

For the Kaplan Meier analyses, the time from randomization to the end of the consolidation phase for participants who do not reach the end of the consolidation phase will be censored at the date of the Week 36 assessment for participants who complete the double-blind period. Participants who withdraw from the study or are lost to follow-up before the Week 36 assessment will be censored at the last visit date after which disease state could not be assessed (ie, at the last non-missing disease state clinical assessment).

All the data in the double-blind period will be included.

3.4.8 Change from baseline in BPDAI activity score at Week 16

The same derivation rules and the same intercurrent events described for the key secondary analysis on the change from baseline in BPDAI activity score at Week 36 will be applied for the analysis of the change from baseline in BPDAI activity score at Week 16.

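### On its more natural reading, SAP 3.3.1 scores a completer whose disease was never controlled as relapse-free, a success on the second gated test

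*SAP*

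**What the plan says.** **Responder rule.** SAP 3.3.1 sets up a binary endpoint "where participants who remain relapse-free throughout the study up to Week 36 will be considered responders"; everyone else is a non-responder. Besides relapse itself, it names these failures: an OCS increase to treat BP after disease control, restricted medication that qualifies as an intercurrent event, withdrawal, and missing data. Protocol 9.4.2.2 and Protocol Table 10 handle the same events the same way.

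**Disease states.** Investigators are asked to "determine their BP disease state (ie, active disease, disease control, end of consolidation phase, remission, and relapse". Protocol 8.1.1.1 adds that the state "will be considered 'active disease' until one of the disease states in" Protocol Table 6 is reached.

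**OCS.** Protocol 4.1.2 says: "In participants who do not achieve disease control, the OCS dose can be increased". Protocol Table 10, footnote a, says: "Rescue with OCS is defined as needing to increase OCS dose after previously having achieved disease control". SAP 3.1.5.1 ties rescue to prior control in the same way.

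**Never controlled.** SAP 3.4.7 foresees completers who do not reach control. In the Kaplan-Meier analysis of time to disease control, those "who do not reach disease control will be censored at the date of the Week 36 assessment for participants who complete the double-blind period". SAP 3.3.1 has no counterpart.

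**Position.** SAP 4.1.1 places this endpoint second of six; testing stops if it fails.

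**The concern.** The composite strategy is meant to turn unfavourable courses into failures. As written, a participant who gains control and later needs more OCS for BP fails. A participant who never gains control, even after OCS increases, can pass.

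That reverses the clinical order of the two outcomes on a confirmatory test that gates four others. The supportive analysis of time to first relapse has the same feature, because SAP 3.3.1 censors anyone without a relapse at the last assessment showing them relapse-free. The Week 16 endpoint (SAP 3.4.5) inherits the rules, and more participants may still be uncontrolled at that point. If the scoring is settled only after unblinding, it becomes a post hoc choice on a controlled test.

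**Working it through.** **Step 1: follow one participant through the rules.** Take a participant recorded in active disease at every visit to Week 36, with no qualifying restricted medication, no withdrawal and no missing Week 36 data.

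- Relapse: none need be recorded, because active disease is a different state and remains the default until another state is reached.
- OCS rescue: an increase before control does not qualify. Protocol 9.4.2.2 limits the event to "rescue use with OCS after having previously achieved disease control".
- Restricted medication, withdrawal, missing data: none applies.
- Result: responder.

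**Step 2: test the alternative reading.** In Protocol 9.1, Protocol 9.4.2.2 and SAP 3.3.1, semicolons separate the three limbs of the relapse definition. The closing condition about achieved control could therefore attach only to the third limb, so that three or more new lesions per month before control would count as relapse. This is less likely, since participants still forming lesions early in treatment would relapse before treatment had worked. Protocol 4.2 also describes the endpoint as "the proportion of participants who have relapsed after tapering steroid therapy (the first key secondary variable". Even on this reading, a never-controlled participant with fewer than three new lesions per month and no large lesion, or with itch alone, would still pass.

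**Step 3: look for a planned analysis that rescores the group.** SAP 4.2.7.5 and 8.1 vary missing data, restricted medication, OCS increase and treatment discontinuation. None rescores a never-controlled completer who stays on IP.

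**Step 4: reproduce the plan's own figure.** SAP 1.3 states 85% power for the primary endpoint (50% versus 20%, 50 per arm, two-sided 5%). This reproduces at 84.8% with a continuity correction and 85.3% with Fisher's exact test; the uncorrected formula gives 89.4%. The documents give no rate or power for the relapse-free endpoint.

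**Step 5: illustrate the size.** Inputs:

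- 50 per arm (SAP 1.3).
- Placebo 33%: the relapse-free figure for placebo in the cited mepolizumab trial (SAP 1.3).
- Benralizumab 63% = 33% + 30 points. The gap is borrowed from the primary endpoint and is an assumption here.
- Never-controlled completers: 0% to 4%, that is 0 to 2 of 50 per arm. This is an assumption; the documents give no Week 36 rate.

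Power is the sum, over all pairs (i, j) of responder counts for which the test favours benralizumab, of Bin(i; 50, p_B) × Bin(j; 50, p_P). The test is Pearson chi-square without correction, z = (i − j)/50 ÷ √(2m(1 − m)/50) with m = (i + j)/100, significant if z > 1.96. It approximates the planned logistic model.

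| Never controlled, benralizumab / placebo | Scored rates | Power |
|---|---|---|
| 0% / 0% | 63% v 33% | 87.5% |
| 0% / 2% | 63% v 35% | 82.6% |
| 0% / 4% | 63% v 37% | 76.7% |
| 2% / 0% | 65% v 33% | 91.4% |
| 4% / 0% | 67% v 33% | 94.3% |
| 2% / 2% | 65% v 35% | 87.5% |
| 4% / 4% | 67% v 37% | 87.5% |

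With equal rates power is unchanged, but both proportions are overstated by 2 or 4 points.

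**Step 6: one participant in a close result.**

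- 27/50 v 17/50: z = 0.20 ÷ √(2 × 0.44 × 0.56/50) = 2.01, p = 0.044.
- One never-controlled placebo completer scored as a responder, 27/50 v 18/50: z = 0.18 ÷ √(2 × 0.45 × 0.55/50) = 1.81, p = 0.070.
- In the other direction, 26/50 v 17/50 has z = 0.18 ÷ √(2 × 0.43 × 0.57/50) = 1.82, p = 0.069. One such benralizumab completer makes it 27/50 v 17/50, p = 0.044.

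At 63% versus 33%, exactly one such completer on placebo removes significance in 4.7% of trials; exactly one on benralizumab creates it in 3.7%.

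**The case against.** **The group is a narrow residue.** This stands. Control needs only that new lesions stop and old ones begin to heal, or that itch starts to ease, and OCS may be increased to reach it. The one control rate in the documents is 91% at 3 weeks on OCS (Protocol 2.2.1). Many persistent failures already leave through restricted medication for BP, withdrawal or missing data, all scored as not relapse-free.

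**The text is ambiguous rather than wrong.** This stands in part. A reader might infer that the SAP requires success for these participants. The semicolons prevent so firm a conclusion. But two readings of a gated endpoint are themselves a reason to specify one.

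**The error is likely to be conservative.** If benralizumab works, never-controlled completers should be more frequent on placebo, which shrinks the difference. A reader might infer a bias in favour of benralizumab; the documents do not support that. Nor do they establish that the two arms will have equal rates.

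**Protocol 8.1.1.1 already fails them.** Its BP Relapse text counts an OCS dose increase as relapse and states no prior-control condition. Read literally, it would catch never-controlled participants whose OCS is increased. It then differs from Table 10, footnote a, and 9.4.2.2; read in context it may presuppose control. Either way it misses those whose OCS is not increased, so it is a separate wording point and does not close the gap.

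**The sensitivity plan is still open.** SAP 8.1.8 allows finalisation before primary lock, and SAP 4.2.7.5 mentions alternative estimands. Neither names this group.

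**Conclusion.** The gap is real and should be fixed. On the more natural reading, observed failure to gain control throughout 36 weeks counts as success on test 2. The confident part is the missing rule; the scoring rests on the more natural of two readings.

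The effect is probably small. The power figures depend on the assumed 63% and 33% and on an assumed 0% to 4% never controlled. They concern test 2 alone, which is confirmatory only if the primary endpoint succeeds. The primary endpoint itself requires complete remission and is unaffected.

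Two stronger inferences are not supported. The 91% figure is a 3-week rate from one study, so its 9% remainder is not a Week 36 never-controlled rate and cannot support a claim of large power loss or false-positive inflation. Nor do the documents settle how a participant not yet controlled should count at Week 16, where a later responder may simply be slow, or what event date should apply in the supportive time-to-relapse analysis. Those are choices to pre-specify.

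**What to change.** Before unblinding:

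1. In SAP 3.3.1 and SAP Table 8, state that relapse is assessed after disease control. State also that participants with no recorded disease control or later favourable state (end of consolidation, partial or complete remission) by Week 36 are classified as not relapse-free under the composite strategy.
2. Report the number of such participants by arm. SAP 4.2.8.7 already summarises time to disease control by arm, so the number can be partly inferred, but an explicit count is clearer.
3. For the Week 16 endpoint (SAP 3.4.5) and the time-to-first-relapse analysis, pre-specify how participants not yet controlled are handled and report their number, for example with a sensitivity analysis.
4. As a separate wording point, reconcile the OCS-increase sentence under BP Relapse in Protocol 8.1.1.1 with Protocol Table 10, footnote a, and Protocol 9.4.2.2.

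The cost is a few SAP sentences, one line in the estimand table and a count by arm, all from data already collected. Item 4 needs a Protocol clarification. Visits and sample size do not change.
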